3.5.3.4 Exposure adjusted analysis

Exposure adjusted incidence rate of ARIA-E events will be summarized based on safety MRI data for the placebo-controlled and LTE active treatment period. The exposure adjusted follow-up time is from the first active dose until the initial occurrence of ARIA-E for those who experienced ARIA-E, and until the end of follow-up for those who did not. Since ARIA is an MRI finding, the day of the last MRI assessment in the placebo-controlled and LTE active treatment period will be used as the end of follow-up for those who didn't experience the event.

Study drug administration information prior to first ARIA-E onset will be summarized for ARIA-E subjects for the placebo-controlled and LTE active treatment period, including number of total infusions, number of infusions at each dose level (placebo, 1 mg/kg, 3 mg/kg, 6 mg/kg and 10 mg/kg), dose level of the last infusion, maximum dose level received, and cumulative dose as a continuous variable.

3.5.3.5 Time to event analysis

Kaplan-Meier plot of time to first ARIA-E event will be produced based on safety MRI data for the placebo-controlled and LTE active treatment period. Only ARIA-E events that occurred during this period will be included. Time to event is calculated as date of the MRI assessment that initially detects the ARIA-E event - date of the first active infusion +1. Censor time for subjects without ARIA-E is calculated as date of the last MRI assessment in the study - date of the first active infusion +1. Estimated proportion with ARIA-E and number of subjects at risk at selected timepoints will also be presented. The plot will be presented by LTE treatment group stratified by ApoE status.

Final V1.0

3.5.4 Clinical Laboratory Data

The following clinical laboratory parameters are assessed in the protocol and will be analyzed:

- Hematology:
 - White blood cells (leukocytes), lymphocytes, neutrophils, monocytes, eosinophils, basophils
 - Red blood cells (erythrocytes), erythrocytes distribution width, erythrocytes mean corpuscular volume, erythrocytes mean corpuscular hemoglobin, erythrocytes mean corpuscular hemoglobin concentration
 - Hemoglobin
 - Hematocrit
 - Platelet count
- Blood chemistry:
 - Liver: alanine aminotransferase (ALT), aspartate aminotransferase (AST), alkaline phosphatase (ALP), total bilirubin, direct bilirubin, gamma-glutamyl-transferase (GGT)
 - Renal: blood urea nitrogen (BUN), creatinine
 - Electrolytes: sodium, potassium, chloride, bicarbonate
 - Other: glucose, calcium, phosphorus, albumin, uric acid, lactate dehydrogenase (LDH), total protein
- O Urinalysis: specific gravity, potential of hydrogen (pH), color, blood, glucose, ketones, protein, white blood cells, red blood cells

3.5.4.1 Quantitative analyses

For numeric laboratory parameters, actual values will be summarized by visit for all the visits in the placebo-controlled and LTE period. Number of evaluable subjects, mean, standard deviation, median, 25% and 75% quartiles, minimum and maximum values will be presented at each visit.

Plots of mean actual values (with standard error) for numeric laboratory parameters at each visit for all the visits in the placebo-controlled and LTE period will be provided.

Summary of change from baseline and percent change from baseline for numeric laboratory parameters will be done on the placebo-controlled and LTE active treatment period. Placebo-controlled baseline will be used for early start subjects and LTE baseline will be used for late start subjects. Change and percent change from baseline will be calculated based on the LTE baseline for late start subjects. Number of evaluable subjects, mean, standard deviation, median, 25% and 75% quartiles, minimum and maximum values will be presented at each visit.

Final V1.0

Listings of individual laboratory measurements by patients for all the parameters will be provided.

Visit windows for by visit summaries

For laboratory by visit summaries, the analysis visit should be defined using visit windows (see Table 5 below). If there is more than 1 value in the same analysis visit window for a certain parameter for a subject, then the closest record to the target visit day will be used for the by visit analysis. If there are 2 values in the same analysis visit window with the same distance from the target visit day for a certain parameter for a subject, then the record with the later date will be used for the by visit analysis. If there are 2 values on the same day for a certain parameter for a subject, then the record with the later time will be used for the by visit analysis.

Table 5: Visit Windows for Laboratory by Visit Summaries

	Analysis visit window ¹			
Analysis visit	For subjects who received	For subjects who received the		
	the first dose of	first dose of aducanumab in		
	aducanumab in the placebo-	the LTE period		
	controlled period	•		
Baseline	Last value prior to the first dose of	Last value prior to the first dose of		
	aducanumab	aducanumab		
Week 24	[2, 252]	[2, 252]		
Week 48	[253, 420]	[253, 420]		
Week 72	[421, 525]	[421, 588]		
Week 78	[526, end day of the placebo-	NA		
	controlled period ²]			
Week 104	[start day of the LTE period ³ , 812]	[589, 868]		
Week 128	[813, 980]	NA		
Week 152	[981, 1148]	[869, 1246]		
Week 176	[1149, 1428]	NA		
Week 232	[1429, 1806]	[1247, 1708]		
Week 284	[1807, 2170]	≥ 1709		
Week 336	≥2171	NA		

^{1.} Visit windows are defined based on days relative to the first dose of aducanumab.

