3.1.2 Analyses period

Depending on the purpose, different analyses will be conducted on the following study periods:

- 1. LTE period. Only data in the LTE period will be included in these analyses. For example, incidence table of adverse events in the LTE period.
- 2. Placebo-controlled and LTE period. All the data in the placebo-controlled and LTE periods will be included in these analyses. For example, mean plot of actual laboratory values in the placebo-controlled and LTE period.
- 3. Placebo-controlled and LTE active treatment period. Active treatment period is defined as the study period(s) that a subject is assigned to aducanumab. For early start subjects subjects who are assigned to aducanumab in both placebo-controlled and LTE period, all the data (placebo-controlled and LTE periods) will be included in the analyses. For late start subjects subjects who are assigned to aducanumab in the LTE period, only data in the LTE period will be included. For example, incidence table of adverse events in the placebo-controlled and LTE active treatment period.

Final V1.0

Subjects to be included in a certain output is determined by both the analysis population and the analysis period. For example, the incidence table of adverse events in the LTE period will include subjects in the safety population for the LTE period, i.e., all randomized subjects who received at least one dose of study treatment in the LTE period. The incidence table of adverse events in the placebo-controlled and LTE active treatment period will include subjects in the safety population for the active treatment period, i.e., all randomized subjects who received at least one dose of study treatment in the active treatment period. In this SAP we do not separately define the analysis population in each analysis period.

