Week 80	[the start day of the LTE period ² , 574]	$[7x -13, 7x+14]$ for $8 \le x \le 252$		
Week x	$[7x -13, 7x+14]$ for $84 \le x \le 176$	$[7x -13, 7x+14]$ for $8 \le x \le 252$		
Week 180	[1247, 1267]	$[7x -13, 7x+14]$ for $8 \le x \le 252$		
Week 182	[1268, 1281]	NA		
Week 184	[1282, 1302]	$[7x -13, 7x+14]$ for $8 \le x \le 252$		
Week 188	[1303, 1330]	$[7x -13, 7x+14]$ for $8 \le x \le 252$		
Week x	$[7x -13, 7x+14]$ for $188 \le x \le 332$	$[7x -13, 7x+14]$ for $8 \le x \le 252$		
Week 256	$[7x -13, 7x+14]$ for $188 \le x \le 332$	[1779, 1799]		
Week 260	$[7x -13, 7x+14]$ for $188 \le x \le 332$	≥ 1800		
•••				
Week 336	[2339, 2359]	NA		

CONFIDENTIAL

Final V1.0

	Analysis visit window ¹			
Analysis visit	For subjects who received the first dose of aducanumab in the placebo-controlled period For subjects who received the first dose of aducanumab in the LTE period			
Week 338	≥ 2360	NA		

- 1. Visit windows are derived based on the first dose of aducanumab.
- 2. The end day of the placebo-controlled period is the last day before the first infusion in LTE for subjects who enter LTE, or the last day in study for subjects who do not enter LTE.
- 3. The start day of the LTE period is the day of first dose in the LTE period.

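### LTE by-visit windows for laboratory and vital-sign values count from the first aducanumab dose, so the two-period summaries of actual values have no place for most placebo-period values of late-start subjects

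*SAP*

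**What the plan says.** The document holds two plans, one for the placebo-controlled period and one for the long-term extension (LTE). The point lies in the LTE SAP.

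- **Scope.** Section 3.5.4.1 says that for numeric laboratory parameters "actual values will be summarized by visit for all the visits in the placebo-controlled and LTE period", and it plans plots of the means with the same scope. Section 3.5.7 plans the same two outputs for vital signs. Section 3.1.2 says of this period: "All the data in the placebo-controlled and LTE periods will be included in these analyses". Its own example is the "mean plot of actual laboratory values in the placebo-controlled and LTE period".
- **Windows.** Sections 3.5.4.1 and 3.5.7 send the by-visit summaries to Tables 5 and 6 and name no other windows. Table 5, footnote 1: "Visit windows are defined based on days relative to the first dose of aducanumab". Table 6, footnote 1: "Visit windows are derived based on the first dose of aducanumab". Each table has one column for subjects first given aducanumab in the placebo-controlled period and one for those first given it in the LTE.
- **Late-start column.** It offers Baseline, the last value before aducanumab, and then windows from day 2 onward. In Table 5 its Week 78 row is marked NA.
- **Day origin elsewhere.** Section 3.5.1 counts days from the first LTE dose only for analyses that use the LTE baseline. It assigns that baseline to outputs on the LTE period and on the active treatment period. Section 3.1 makes the placebo-controlled baseline the default.

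**The concern.** An output defined to contain all data from both periods is tied to windows that cannot hold the placebo period of the late-start groups. A programmer must either depart from Tables 5 and 6 or drop those values.

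If the tables are followed, the two-period displays lose most of the concurrent placebo course. They also put two different study times under one visit label. A reader who takes the week labels as study time would compare late-start values from the extension with early-start values from the first months of the trial.

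**Working it through.** The plan states no figure to reproduce. The check maps scheduled placebo-period days onto the late-start columns.

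**Inputs**
- Laboratory target days: 1 (baseline), 169, 337, 505 and 547 (placebo-controlled SAP, Table 7).
- Vital-sign target days: day 1, then every 4 weeks from Week 4 (day 29) to Week 76 (day 533) (placebo-controlled SAP, Table 10). That is 1 + 19 = 20 values.
- First LTE visit: Week 80 (LTE SAP 3.5.3.2), so day 80 × 7 + 1 = 561. This is nominal. Days 548 and 575 are taken as an assumed range.
- Lowest post-baseline window in both late-start columns: day 2.

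**Laboratory values.** For a day before the first aducanumab dose, relative day = study day − 561.

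| Scheduled value | Study day | Relative day | Late-start column of Table 5 |
|---|---|---|---|
| Study baseline | 1 | −560 | none |
| Week 24 | 169 | −392 | none |
| Week 48 | 337 | −224 | none |
| Week 72 | 505 | −56 | none |
| Week 78 | 547 | −14 | Baseline (last value before aducanumab) |

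So 4 of 5 values have no visit. With a first LTE dose on day 548 the relative days are −547, −379, −211, −43 and −1. On day 575 they are −574, −406, −238, −70 and −28. The result is the same.

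**Vital signs.** The 20 values fall on relative days 1 − 561 = −560 to 533 − 561 = −28. None reaches day 2. At most one becomes Baseline, so at least 19 of 20 have no visit.

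**Visit labels.** A late-start value taken 24 weeks into the LTE falls on study day 561 + 168 = 729, and (729 − 1)/7 = 104 weeks. The late-start Week 24 window of Table 5, relative days 2 to 252, covers study days 2 + 560 = 562 to 252 + 560 = 812. The early-start column calls that same stretch Week 104: it runs from the start of the LTE to day 812.

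**Subjects with no day origin.** About 1605/3 = 535 subjects are planned for placebo. LTE groups are assigned at randomisation whether or not the subject enters the LTE (LTE SAP 2.1), so those who do not enter still belong to a late-start group. If they receive no aducanumab they have no Day 1 and fit neither column. Their number is not given.

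**After the change.** Counted from the first infusion of study treatment, days 169, 337, 505 and 547 fall in [2, 252], [253, 420], [421, 525] and the window opening at day 526. These are Weeks 24, 48, 72 and 78, the same windows as Table 7 of the placebo-controlled SAP. The original baseline is kept as well.

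**The case against.** The strongest reply is that LTE SAP 3.5.1 already settles the matter. The two-period summaries of actual values use no LTE baseline, so the LTE day origin should not apply to them. The two-period efficacy and PET windows (LTE SAP Tables 3 and 4) use one day scale for all groups. On this view the footnotes were merely left without a limit. This stands as evidence of intent, and it makes the point a conflict of wording rather than a wrong choice of analysis. It does not remove the conflict: the footnotes carry no exception, the late-start column has no placebo-period windows, and for windows neither section refers back to the placebo-controlled SAP.

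Some stronger conclusions might be inferred, and the documents do not support them:

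- **That the placebo arm vanishes from the plots.** Late-start groups stay in every display from their LTE baseline onward, and that baseline is a value from before any aducanumab. What is lost is the earlier course.
- **That drift over study time cannot be told from drug exposure in this trial.** The placebo-controlled SAP (4.5.4.1 with Table 7, 4.5.7 with Table 10) summarises and plots both kinds of data by visit with the placebo group alongside. LTE listings also cover both periods.
- **That laboratory signal detection suffers.** The qualitative analyses in LTE SAP 3.5.4.2 use all values within their stated period, not the windowed record.
- **That time since first active dose is itself a wrong scale.** It suits the change-from-baseline summaries on the active treatment period. The LTE immunogenicity windows (LTE SAP Table 7) carry the same footnote but serve only that period, so they are not affected.
- **That all 535 planned placebo subjects are affected.** That is an upper figure. Placebo subjects given aducanumab by accident in the placebo-controlled period fall in the first column by its heading.

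**Conclusion.** The point holds, and it is minor. Tables 5 and 6 of the LTE SAP, followed as written, contradict the stated scope of the two-period summaries and plots of actual values, and they contradict the day-origin rule in section 3.5.1. For each late-start subject, 4 of 5 scheduled laboratory values and at least 19 of 20 vital-sign values from the placebo-controlled period have no visit. The week labels of the two start groups differ by about 80 weeks of study time.

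The counts assume that visits fall on their target days and that the first LTE dose is near day 561. The laboratory count does not change between days 548 and 575. No hypothesis test, estimand or decision rule depends on these displays.

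**What to change.** In LTE SAP 3.5.4.1 and 3.5.7, state that outputs on the combined placebo-controlled and LTE period use the first window column of Tables 5 and 6 for every subject, with Day 1 as the first infusion of study treatment, whether aducanumab or placebo. The Baseline row for those outputs should likewise mean the last value before that infusion. Limit the late-start column, counted from the first aducanumab dose, to outputs on the active treatment period, and say so in footnote 1 of each table.

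The cost is a sentence and a footnote. The first-infusion date already serves as the day origin in the placebo-controlled SAP, so no new data are needed.

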3.5.4.2 Qualitative analyses

For qualitative analyses, all values will be included (not just the "analyzed record" within each visit window in the quantitative analyses).

Shift analyses

^{2.} The end day of the placebo-controlled period is the last day before the first infusion in LTE, or the last day in study for subjects who do not enter LTE.

^{3.} The start day of the LTE period is the day of first infusion in LTE period.

Final V1.0

Laboratory data will be summarized using shift tables where appropriate for the placebocontrolled and LTE active treatment period. Each subject's hematology, blood chemistry and urinalysis numeric values will be flagged as "low", "normal", or "high" relative to the normal ranges of the central laboratory or as "unknown" if no result is available. Each subject's urinalysis categorical values will be flagged as "positive" or "negative", or "unknown" if no value is available.

Shifts from baseline to high/low status will be presented for hematology, blood chemistry and urinalysis numeric parameters, and shifts from baseline to abnormal (positive) will be presented for urinalysis categorical parameters. Shift to low includes normal to low, high to low, and unknown to low; Shift to high includes normal to high, low to high, and unknown to high. Subjects need to have at least one post-baseline evaluation and a baseline value not low or high or positive (including missing) in order to be included in the analysis.

For early start subjects, the placebo-controlled baseline will be used and shifts that occurred in either placebo-controlled or LTE period will be included. For late start subjects, the LTE baseline will be used and shifts that occurred in the LTE period based on LTE baseline will be included.

Grade analyses

Worst post-baseline grade will be summarized for each laboratory parameter in both exclusive way and cumulative way for the placebo-controlled and LTE active treatment period. Subjects need to have at least one post-baseline evaluation in the active treatment period in order to be included in the analysis. Common Toxicity Criteria for Adverse Events v4.0.3 (CTCAE) published on 2010-06-14 will be used for grade determination. Grade determination is based solely on laboratory values not taking AEs into account.

Potentially Clinically Significant laboratory abnormalities analyses

Please refer to the placebo-controlled SAP for the parameters and criteria for potentially clinically significant laboratory abnormalities analyses.

The number of subjects with potentially clinically significant laboratory abnormalities post-baseline will be summarized for the placebo-controlled and LTE active treatment period.

Subjects need to have at least one post-baseline evaluation in the active treatment period and a baseline value not potentially clinically significant (including missing) in order to be included in the analysis.

Same as the shift analysis, for early start subjects, the placebo-controlled baseline will be used and abnormalities that occurred in either placebo-controlled or LTE period will be included. For late start subjects, the LTE baseline will be used and PCS abnormalities that occurred in the LTE period based on LTE baseline will be included.

Potential serious hepatotoxicity

In this SAP, we define potential serious hepatotoxicity as ALT or AST > 3x ULN and total bilirubin > 2x ULN at any time post-baseline in the placebo-controlled and LTE active CONFIDENTIAL

Final V1.0

treatment period (not necessarily concurrent). A scatterplot of the maximum post-baseline ALT or AST value relative to ULN and maximum post-baseline total bilirubin value relative to ULN (not necessarily concurrent) for each subject will be provided. A line plot of ALT, AST, ALK and total bilirubin values over time in the active treatment period for subjects with potential serious hepatotoxicity will be provided. In addition, subjects with ALT > 1x ULN, >3x ULN, >5x ULN, >5x ULN, >10x ULN or >20x ULN, subjects with AST > 1x ULN, >3x ULN, >5x ULN, >10x ULN or >20x ULN, subjects with total bilirubin >1x ULN or >2x ULN, subjects with ALP >1x ULN or >1.5x ULN, and subjects with AST or ALT > 3x ULN post-baseline accompanied by concurrently elevated total bilirubin >1.5x ULN or > 2x ULN in the active treatment period will be presented. Concurrent is defined as on the same day. A listing of subjects with potential serious hepatotoxicity will be provided.

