4.5.4.2 Qualitative analyses

For all qualitative analyses, all values will be included (not just the "analyzed record" within each visit window in the quantitative analyses).

Shift analyses

Laboratory data will be summarized using shift tables where appropriate. Each subject's hematology, blood chemistry and urinalysis numeric values will be flagged as "low", "normal", or "high" relative to the normal ranges of the central laboratory or as "unknown" if no result is available. Each subject's urinalysis categorical values will be flagged as "positive" or "negative", or "unknown" if no value is available.

Shifts from baseline to high/low status will be presented for hematology, blood chemistry and urinalysis numeric parameters, and shifts from baseline to abnormal (positive) will be presented for urinalysis categorical parameters. Shift to low includes normal to low, high to low, and unknown to low; Shift to high includes normal to high, low to high, and unknown to high. Subjects need to have at least one post-baseline evaluation and a baseline value not low or high or positive (including missing) in order to be included in the analysis. A listing of laboratory normal ranges will be provided.

Grade analyses

Worst post-baseline grade will be summarized for each laboratory parameter in both exclusive way and cumulative way. Subjects need to have at least one post-baseline evaluation in order to be included in the analysis. Common Toxicity Criteria for Adverse Events v4.0.3 (CTCAE) published on 2010-06-14 will be used for grade determination. Grade determination is based solely on laboratory values not taking AEs into account.

Potentially Clinically Significant laboratory abnormalities analyses

For hematology, blood chemistry and urinalysis, the number of subjects with potentially clinically significant laboratory abnormalities post-baseline will be summarized for the parameters provided in Table 8. Subjects need to have at least one post-baseline evaluation and a baseline value not potentially clinically significant (including missing) in order to be included in the analysis.

Table 8: Criteria to Determine Potentially Clinically Significant (PCS) Laboratory Abnormalities

Clinical Laboratory Outlier Criteria			
Parameter name	PCS Low	PCS High	
HEMATOLOGY			

Final V1.0

Clinical Laboratory Outlier Criteria				
Parameter name	PCS Low	PCS High		
White blood cells	<3.0 x 10 ⁹ /L	$>16 \times 10^9/L$		
Lymphocytes	<0.8 x 10 ⁹ /L	>12 x 10 ⁹ /L		

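### Laboratory grade tables take no account of baseline grade, so stable pre-existing grades are counted together with new or worsened ones

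*SAP*

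**What the plan says.** Under Grade analyses, LTE SAP 3.5.4.2 states: "Worst post-baseline grade will be summarized for each laboratory parameter in both exclusive way and cumulative way". The entry condition is: "Subjects need to have at least one post-baseline evaluation in the active treatment period in order to be included in the analysis". Placebo-controlled SAP 4.5.4.2 plans the same summary with an equivalent condition: "Subjects need to have at least one post-baseline evaluation in order to be included in the analysis". Both use CTCAE v4.0.3, and "Grade determination is based solely on laboratory values not taking AEs into account". Neither paragraph mentions the grade at baseline.

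The neighbouring categorical analyses do use it. The shift tables require "a baseline value not low or high or positive (including missing) in order to be included in the analysis". The PCS tables require "a baseline value not potentially clinically significant (including missing) in order to be included in the analysis". For both, LTE SAP 3.5.4.2 also states that early-start subjects are referred to the placebo-controlled baseline and late-start subjects to the LTE baseline.

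**The concern.** A worst-grade table is naturally read as showing how severe laboratory abnormalities became on treatment. As specified, it shows how severe they were after baseline, whether or not they were already there. The rest of the safety plan takes more care: adverse events must have begun or got worse after the first infusion (placebo-controlled SAP 4.5.2, LTE SAP 3.5.2), and the shift and PCS tables remove subjects already abnormal at baseline. The grade paragraphs apply neither principle and give no reason.

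At stake is whether the reader can see worsening in subjects who entered with an abnormal value. The grade table is the natural place for it, but there those subjects are merged with subjects who did not change.

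**Working it through.** The plans state no figure to reproduce, so the main check compares the laboratory analyses by what each can show.

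| Analysis | Baseline condition | New abnormality from normal baseline | Worsening from abnormal baseline |
|---|---|---|---|
| Shift (4.5.4.2; LTE 3.5.4.2) | Baseline not already abnormal; missing allowed | Shown | Same-direction worsening not shown |
| PCS (Table 8) | Baseline not already PCS; missing allowed | Shown if the limit is crossed | Shown only if baseline was outside the normal range but not PCS, and the value then crosses the limit |
| Liver multiples of ULN | None | Mixed with pre-existing | Mixed with pre-existing |
| Worst grade | None | Mixed with pre-existing | Mixed with pre-existing |
| Change and percent change | Numeric difference | Group summary by visit | Group summary by visit |

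**Shift.** Shift to high accepts normal, low or unknown at baseline. A subject already high who climbs further is not counted.

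**PCS.** Table 8 has at most one limit per direction for each parameter. GGT, direct bilirubin, LDH and uric acid are listed for analysis (placebo-controlled SAP 4.5.4, LTE SAP 3.5.4) but do not appear in Table 8. For these four, no categorical analysis refers same-direction worsening from an abnormal baseline back to that baseline.

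**Columns.** Analysis display A of the LTE SAP has late-start, early-start and total columns, all on aducanumab. Nothing in the active-treatment grade table indicates how much of a rate was present before the first active dose.

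**Illustration of dilution, with assumed rates.** Let b be the share with grade 1 or more at baseline who keep it, and i the incidence of a new grade 1 or more among the rest. The table then shows

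P = b + (1 − b) × i.

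Assume i = 10% in one group and 5% in the other (ratio 2.0, difference 5 points), with the same b in both groups.

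| b | Group 1 | Group 2 | Ratio | Difference |
|---|---|---|---|---|
| 5% | 0.05 + 0.95 × 0.10 = 14.5% | 0.05 + 0.95 × 0.05 = 9.75% | 1.49 | 4.75 points |
| 10% | 0.10 + 0.90 × 0.10 = 19.0% | 0.10 + 0.90 × 0.05 = 14.5% | 1.31 | 4.5 points |
| 30% | 0.30 + 0.70 × 0.10 = 37.0% | 0.30 + 0.70 × 0.05 = 33.5% | 1.10 | 3.5 points |
| 50% | 0.50 + 0.50 × 0.10 = 55.0% | 0.50 + 0.50 × 0.05 = 52.5% | 1.05 | 2.5 points |

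The share of counted subjects who are new is (1 − b) × i / P. At i = 5% it is 0.0475/0.0975 = 48.7% for b = 5%, 0.045/0.145 = 31.0% for b = 10% and 0.035/0.335 = 10.4% for b = 30%.

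**The case against.** The best defence is that the table does what its title says. It is a descriptive summary of worst post-baseline grade, not labelled treatment-emergent, and it is one view among several. Shift and PCS tables isolate new abnormalities, "Summary of change from baseline and percent change from baseline for numeric laboratory parameters" is planned, and all individual values are listed. This stands for subjects with a normal baseline. A reader might infer that the plan as a whole hides new laboratory abnormalities; it does not. The defence fails for subjects abnormal at baseline, where the shift and PCS tables are incomplete, visit means do not show individual worsening, and a listing is not an analysis.

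Other strong readings also lack support:
- Grade is not the only severity-ordered laboratory output. ALT, AST, total bilirubin and ALP are counted at rising multiples of ULN, though also without a baseline condition.
- The LTE baseline is not ignored. The general rule in LTE SAP 3.5.1 makes it the baseline for late-start subjects in active-treatment analyses, so it fixes which values are post-baseline. What is missing is comparison with the grade at that point.
- Different counts in the grade, shift and PCS tables would not be a contradiction, because the thresholds and denominators differ by definition.

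Finally, the dilution figures rest on assumed rates and concern grade 1 or more. Stable low grades do not enter the cumulative higher-grade rows, no ratio or test of grades is planned, and the loss is milder on the difference scale. All of this stands and limits the size of the point.

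**Conclusion.** The point holds as a minor weakness in safety reporting. Followed as written, both grade analyses count stable pre-existing grades with new or worsened ones. In the placebo-controlled period randomisation should balance baseline grades, so the expected effect is dilution rather than bias. In the LTE active-treatment tables the background cannot be judged at all.

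The substantive gap is worsening from an already abnormal baseline, and it is clearest for GGT, direct bilirubin, LDH and uric acid. The size of the dilution cannot be derived from the documents: it depends on the share with a persistent baseline grade, which the plans do not give and which will differ by parameter. No efficacy inference is affected.

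**What to change.** In placebo-controlled SAP 4.5.4.2 and LTE SAP 3.5.4.2, present baseline grade by worst post-baseline grade for each graded parameter, and add a count of subjects whose grade rose above the applicable baseline. In the LTE SAP that is the placebo-controlled baseline for early-start and the LTE baseline for late-start subjects. Treat a missing baseline as grade 0, in line with the shift and PCS rules, which both admit missing baselines. Keep the existing worst-grade rows so that stable high grades remain visible; counting only increases would remove them from the table.

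The cost is a sentence in each SAP, one derived variable and a somewhat larger table. The data are already collected. The change helps only where CTCAE assigns a grade; the SAPs do not say for which of the listed parameters it does.
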